4.2.1 Dose Selection/Modification

The rationale for selection of doses to be used in this trial is provided in Section 1.

On Day 1 of each three - week cycle, patients will receive 25 mcg of paricalcitol or placebo intravenously followed ≥ 30 minutes later by 200 mg of pembrolizumab infused over 30

minutes. Patients will then receive 25 mcg of paricalcitol or placebo intravenously on days 3, 5, 8, 10, 12, 15, 17, 19 (± 1 day) of each 21 day cycle.

Details on preparation and administration of pembrolizumab are provided in the Pharmacy Manual.

4.2.2 Paricalcitol (Zemlar[®]) and Placebo

Dosage Form: Paricalcitol is available as a sterile, clear, colorless aqueous solution for injection, in concentrations of 2mcg/mL and 5mcg/mL. Each site will be using their local pharmacy supply of paricalcitol and will use the necessary volume for the given concentration and per the product labeling instructions (Appendix 2) to administer a total dose of 25mcg. Patients will receive either paricalcitol or the equivalent volume of placebo (saline solution) intravenously at each dosing point.

The doses will be prepared in an aseptic manner and documented by the unblinded Pharmacist just prior to dosing. Documentation relating to this preparation will be available for independent monitoring and verification.

Further details of preparation are provided in the Pharmacy manual.

There must be ≥ 30 minutes in between the completion of the paricalcitol injection and the start of the pembrolizumab infusion.

Note: The same IV line may be used to administer both the paricalcitol and the pembrolizumab. However there must be at least 30 minutes in between the completion of the paricalcitol injection and the start of the pembrolizumab infusion. Sites should use normal saline to keep line open for this period in between paricalcitol injection and subsequent pembrolizumab infusion.

4.2.3 Pembrolizumab (Keytruda[®])

Dosage Form: Pembrolizumab Solution for Infusion, 100 mg/ 4 mL vial to be stored under refrigerated conditions (2 – 8 °C (36 °F to 46 °F)) and protected from light in the original container and outer box.

Pembrolizumab Solution for Infusion is a sterile, non-pyrogenic aqueous solution supplied in single-use Type I glass vial containing 100 mg/4 mL of pembrolizumab. The product is preservative-free solution which is essentially free of extraneous particulates.

Preparation and Storage for Intravenous Infusion:

Specific instructions on the aseptic technique used to prepare the intravenous solution will be provided in a Pharmacy manual.

In summary the process will involve:

- Two vials of pembrolizumab solution will be used for each infusion. Each vial is 100mg/4 mL.
- Infusion solutions will be prepared in 0.9% Sodium Chloride Injection, USP (normal saline). Pembrolizumab **SHOULD NOT BE MIXED WITH OTHER DILUENTS**.
- The diluted solution will be mixed by gentle inversion, should not contain visible particulate matter or discoloration and should not be frozen.
- When removed from refrigeration the vials of solution and/or the prepared infusion may be stored at room temperature for a cumulative total of 6 hours only. This time includes the time of the infusion.
- The prepared infusion IV bags may be stored under refrigeration at 2 °C to 8 °C (36 °F to 46 °F) for up to 24 hours. If refrigerated, allow the IV bags to come to room temperature prior to use and the infusion should be completed within 6 hours.
- Specific materials for infusion bags and infusion sets are approved for administration of pembrolizumab. A list of approved materials is provided in the Pharmacy manual.
- **There must be 30 minutes in between the completion of the paricalcitol injection and the start of the pembrolizumab infusion.**
- The solution is slowly infused over a period of 30 minutes through an approved IV line with no other drugs co-administered through the same line.

The infusions will be prepared and documented by the unblinded pharmacist just prior to dosing. Documentation relating to this preparation will be available for independent monitoring and verification.

4.2.4 Dose Modification (Escalation/Titration/Other) of Pembrolizumab (Keytruda®) in cases of Toxicity

AEs associated with pembrolizumab exposure may represent an immunologic etiology. These immune-related AEs (irAEs) may occur shortly after the first dose or several months after the last dose of pembrolizumab treatment and may affect more than one body system simultaneously. Therefore, early recognition and initiation of treatment is critical to reduce complications. Based on existing clinical study data, most irAEs were reversible and could be managed with interruptions of pembrolizumab, administration of corticosteroids and/or other supportive care. For suspected irAEs, ensure adequate evaluation to confirm etiology or exclude other causes. Additional procedures or tests such as bronchoscopy, endoscopy, skin biopsy may be included as part of the evaluation. Based on the severity of irAEs, withhold or permanently discontinue pembrolizumab and administer corticosteroids. Dose modification and toxicity management guidelines for irAEs associated with pembrolizumab are provided in Table 4.

Table 4. Dose Modification and Management Guidelines for Drug-Related Adverse Events

| General instructions: | | | | |
|---|--|--------------------------------------|---|---|
| 
 1. Corticosteroid taper should be initiated upon AE improving to Grade 1 or less and continue to taper over at least 4 weeks. 2. For situations where pembrolizumab has been withheld, pembrolizumab can be resumed after AE has been reduced to Grade 1 or 0 and corticosteroid has been tapered. Pembrolizumab should be permanently discontinued if AE does not resolve within 12 weeks of last dose or corticosteroids cannot be reduced to ≤ 10 mg prednisone or equivalent per day within 12 weeks. 3. For severe and life-threatening irAEs, IV corticosteroid should be initiated first followed by oral steroid. Other immunosuppressive treatment should be initiated if irAEs cannot be controlled by corticosteroids. | | | | |
| irAEs | Toxicity grade or conditions (NCI CTCAE v4.0) | Action taken to pembrolizumab | irAE management with corticosteroid and/or other therapies | Monitor and follow-up |
| Pneumonitis | Grade 2 | Withhold | 
 • Administer corticosteroids (initial dose of 1-2 mg/kg prednisone or equivalent) followed by taper | 
 • Monitor participants for signs and symptoms of pneumonitis • Evaluate participants with suspected pneumonitis with radiographic imaging and initiate corticosteroid treatment • Add prophylactic antibiotics for opportunistic infections |
| | Grade 3 or 4, or recurrent grade 2 | Permanently discontinue | | |
| Diarrhea / colitis | Grade 2 or 3 | Withhold | 
 • Administer corticosteroids (initial dose of 1-2 mg/kg prednisone or equivalent) followed by taper | 
 • Monitor participants for signs and symptoms of enterocolitis (i.e. diarrhea, abdominal pain, blood or mucus in stool with or without fever) and of bowel perforation (i.e. peritoneal signs and ileus). • Participants with \geqGrade 2 diarrhea suspecting colitis should consider GI consultation and performing endoscopy to rule out colitis. • Participants with diarrhea/colitis should be advised to drink liberal quantities of clear fluids. If sufficient oral fluid intake is not feasible, fluid and electrolytes should be substituted via IV infusion. |
| | Grade 4 | Permanently discontinue | | |

| | | | | |
|--|--|--|---|---|
| AST / ALT elevation or Increased Bilirubin | Grade 2 | Withhold | 
 Administer corticosteroids (initial dose of 0.5-1 mg/kg prednisone or equivalent) followed by taper | 
 Monitor with liver function tests (consider weekly or more frequently until liver enzyme value returned to baseline or is stable) |
| | Grade 3 or 4 | Permanently discontinue | 
 Administer corticosteroids (initial dose of 1-2 mg/kg prednisone or equivalent) followed by taper | |
| Type 1 diabetes mellitus (T1DM) or Hyperglycemia | Newly onset T1DM or Grade 3 or 4 hyperglycemia associated with evidence of β -cell failure | Withhold | 
 Initiate insulin replacement therapy for participants with T1DM Administer anti-hyperglycemic in participants with hyperglycemia | 
 Monitor participants for hyperglycemia or other signs and symptoms of diabetes. |
| Hypophysitis | Grade 2 | Withhold | 
 Administer corticosteroids and initiate hormonal replacements as clinically indicated. | 
 Monitor for signs and symptoms of hypophysitis (including hypopituitarism and adrenal insufficiency) |
| | Grade 3 or 4 | Withhold permanently discontinue ¹ or | | |
| Hyperthyroidism | Grade 2 | Continue | 
 Treat with non-selective beta-blockers (e.g. propranolol) or thionamides as appropriate | 
 Monitor for signs and symptoms of thyroid disorders. |
| | Grade 3 or 4 | Withhold Permanently discontinue ¹ or | | |
| Hypothyroidism | Grade 2-4 | Continue | 
 Initiate thyroid replacement hormones (e.g. levothyroxine or liothyronine) per standard of care | 
 Monitor for signs and symptoms of thyroid disorders. |
| Nephritis and renal dysfunction | Grade 2 | Withhold | 
 Administer corticosteroids (prednisone 1-2 mg/kg or equivalent) followed by taper. | 
 Monitor changes of renal function. |
| | Grade 3 or 4 | Permanently discontinue | | |

| | | | | |
|-----------------|---------------------------------------|---|--|---|
| Myocarditis | Grade 1 or 2 | Withhold | 
 Based on severity of AE administer corticosteroids | 
 Ensure adequate evaluation to confirm etiology and/or exclude other causes. |
| | Grade 3 or 4 | Permanently discontinue | | |
| All Other irAEs | Intolerable/ persistent Grade 2 | Withhold | 
 Based on severity of AE administer corticosteroids | 
 Ensure adequate evaluation to confirm etiology or exclude other causes |
| | Grade 3 | Withhold or discontinue based on the type of event. Events that require discontinuation include and not limited to: Guillain-Barré Syndrome, encephalitis | | |
| | Grade 4 or recurrent Grade 3 | Permanently discontinue | | |

1. Withhold or permanently discontinue pembrolizumab is at the discretion of the investigator or treating physician.

NOTE: For participants with Grade 3 or 4 immune-related endocrinopathy where withhold of pembrolizumab is required, pembrolizumab may be resumed when AE resolves to \leq Grade 2 and is controlled with hormonal replacement therapy or achieved metabolic control (in case of T1DM).

Dose modification and toxicity management of infusion-reactions related to pembrolizumab
Pembrolizumab may cause severe or life threatening infusion-reactions including severe hypersensitivity or anaphylaxis. Signs and symptoms usually develop during or shortly after drug infusion and generally resolve completely within 24 hours of completion of infusion. Dose modification and toxicity management guidelines on pembrolizumab associated infusion reaction are provided in Table 5.

Table 5. Pembrolizumab Infusion Reaction Dose modification and Treatment Guidelines

| NCI CTCAE Grade | Treatment | Premedication at Subsequent Dosing |
|---|---|---|
| Grade 1 Mild reaction; infusion interruption not indicated; intervention not indicated | Increase monitoring of vital signs as medically indicated until the participant is deemed medically stable in the opinion of the investigator. | None |
| Grade 2 Requires therapy or infusion interruption but responds promptly to symptomatic treatment (eg, antihistamines, NSAIDs, narcotics, IV fluids); prophylactic medications indicated for ≤24 hrs | Stop Infusion. Additional appropriate medical therapy may include but is not limited to: 
 • IV fluids • Antihistamines • NSAIDs • Acetaminophen • Narcotics Increase monitoring of vital signs as medically indicated until the participant is deemed medically stable in the opinion of the investigator. If symptoms resolve within 1 hour of stopping drug infusion, the infusion may be restarted at 50% of the original infusion rate (eg, from 100 mL/hr to 50 mL/hr). Otherwise dosing will be held until symptoms resolve and the participant should be premedicated for the next scheduled dose. Participants who develop Grade 2 toxicity despite adequate premedication should be permanently discontinued from further study drug treatment | Participant may be premedicated 1.5 h (±30 minutes) prior to infusion of pembrolizumab with: 
 • Diphenhydramine 50 mg PO (or equivalent dose of antihistamine). • Acetaminophen 500-1000 mg PO (or equivalent dose of analgesic). |
| Grades 3 or 4 Grade 3: Prolonged (ie, not rapidly responsive to symptomatic medication and/or brief interruption of infusion); recurrence of symptoms following initial improvement; hospitalization indicated for other clinical sequelae (eg, renal impairment, pulmonary infiltrates) Grade 4: Life-threatening; pressor or ventilatory support indicated | Stop Infusion. Additional appropriate medical therapy may include but is not limited to: 
 • Epinephrine** • IV fluids • Antihistamines • NSAIDs • Acetaminophen • Narcotics • Oxygen • Pressors • Corticosteroids Increase monitoring of vital signs as medically indicated until the participant is deemed medically stable in the opinion of the investigator. Hospitalization may be indicated. **In cases of anaphylaxis, epinephrine should be used immediately. Participant is permanently discontinued from further study drug treatment. | No subsequent dosing |
| Appropriate resuscitation equipment should be available at the bedside and a physician readily available during the period of drug administration. For further information, please refer to the Common Terminology Criteria for Adverse Events v4.0 (CTCAE) at http://ctep.cancer.gov | | |

4.2.4.1 *Other allowed dose interruption for pembrolizumab*

Pembrolizumab may be interrupted for situations other than treatment-related AEs such as medical / surgical events or logistical reasons not related to study therapy. Participants should be placed back on study therapy within 3 weeks of the scheduled interruption, unless otherwise discussed with the Sponsor. The reason for interruption should be documented in the patient's study record.

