- Symptoms of endocrinopathies, including hypophysitis (including hypopituitarism and secondary adrenal insufficiency), thyroid disorders (hypo or hyperthyroidism and thyroiditis), Type 1 diabetes mellitus, rapid heart rate, change in weight, increased sweating, hunger and/or thirst, frequent urination, hair loss, feeling cold, constipation, deeper voice, muscle aches, unusual and persistent headache, dizziness or fainting.
- Symptoms of nephritis or kidney failure e.g. change in amount or color of urine.
- Symptoms of Guillain-Barre syndrome, pancreatitis, myasthenic syndrome, encephalitis, uveitis, sarcoidosis, and myocarditis (some fatal).

- Symptoms of solid organ transplant rejection, and graft versus host disease (GvHD) in patients who had an allogeneic stem cell transplant after treatment with pembrolizumab.
- Symptoms of other organ issues e.g. rash, changes in eyesight, severe or persistent muscle or joint pain, severe muscle weakness, myositis, severe skin reactions, and anemia. Rarely, severe skin reactions have included cases of Stevens-Johnson syndrome (SJS) and toxic epidermal necrolysis (TEN) some with fatal outcome.
- Symptoms of infusion reactions which may be life-threatening e.g. chills, shaking, shortness of breath, wheezing, itching, rash, flushing, dizziness, fever or feelings of passing out.

Patients with the following may be at particular risk:

- Immune system disorders e.g. Crohn's, ulcerative colitis, lupus.
- Organ transplant – solid organ transplant rejection in donor recipients has been reported. Consider the benefit of treatment with pembrolizumab versus the risk of possible organ rejection in the patients.
- Lung or breathing conditions e.g. interstitial lung disease.
- Liver problems e.g. hepatitis.

The effects of pembrolizumab on unborn fetus and possible transmission through breast milk have not been established. Patients on pembrolizumab should not become pregnant or breast-feed. It is recommended that patients should use adequate birth control and abstain from breast-feeding until at least 4 months after dosing with this product.

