6.1.7.4 Follow-up Period

30-day Follow-up Visit

The mandatory Safety Follow-up visit should be conducted approximately 30 (\pm 5 days) after the last dose of trial treatment and before initiation of a new anti-cancer treatment, whichever comes first.

The following assessments will be performed:

- Serum β -HCG pregnancy test (for WOCBP)
- AEs using the NCI CTCAE Version 4.0 (see Appendix 3)
- Review contraception use as required by protocol Section 4.7.2 (where applicable)
- Confirm contact information for patient and a designated family member and remind patient of FU telephone contact that will be conducted every 90 days for survival status.

All AEs that occur prior to the Safety Follow-Up Visit should be recorded. Patients with an AE of Grade > 1 will be followed until the resolution of the AE to Grade 0-1 or until the beginning of a new anti-cancer therapy, whichever occurs first.

SAEs that occur within 90 days of the end of trial treatment or before initiation of a new anti-cancer treatment should also be followed and recorded.

Survival Follow-up Phase

Once a patient experiences confirmed disease progression or starts a new anti-cancer therapy, the patient moves into the Survival Follow-up Phase and should be contacted by telephone 90 (\pm 5 days) from EOT and every 90 \pm 15 days after that until death, withdrawal of consent, or the end of the trial, whichever occurs first.

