The criteria below are intended as reference guidelines to assist the investigator in assessing the likelihood of a relationship between the trial treatment and the adverse event based upon the available information.

The following components are to be used to assess the relationship between trial treatment and the AE; the greater the correlation with the components and their respective elements (in number and/or intensity), the more likely the trial treatment caused the adverse event (AE):

Exposure: Is there evidence that the patient was actually exposed to trial treatment such as: reliable history, acceptable compliance assessment (pill count, diary, etc.), expected pharmacologic effect, or measurement of drug/metabolite in bodily specimen?

Time Course: Did the AE follow in a reasonable temporal sequence from administration of trial treatment? Is the time of onset of the AE compatible with a drug-induced effect?

Likely Cause: Is the AE not reasonably explained by another etiology such as underlying disease, other drug(s)/vaccine(s), or other host or environmental factors?

Dechallenge: Was trial treatment discontinued or dose/exposure/frequency reduced?

If yes, did the AE resolve or improve? **If yes,** this is a positive dechallenge.

If no, this is a negative dechallenge.

Note: This criterion is not applicable if: (1) the AE resulted in death or permanent disability; (2) the AE resolved/improved despite continuation of the trial treatment; or (3) the trial is a single-dose drug trial); or (4) trial treatment is/are only used one time.

Rechallenge: Was the patient re-exposed to trial treatment in this trial?

If yes, did the AE recur or worsen?

If yes, this is a positive rechallenge.

If no, this is a negative rechallenge.

Note: If a rechallenge is planned for an adverse event which was serious and which may have been caused by either of the trial treatments, or if re-exposure to trial treatment poses additional potential significant risk to the patient, then the rechallenge must be approved in advance by the Sponsor as per dose modification guidelines in the protocol.

Consistency with Trial Treatment Profile: **Is the clinical/pathological presentation of the AE consistent with previous knowledge regarding trial treatment or drug class pharmacology or toxicology?**

| Relationship | Attribution | Description |
|--|-------------|---|

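### The general restart rule in Protocol Table 4 permits pembrolizumab to be resumed at Grade 1 myocarditis, a grade at which the myocarditis row says to withhold it

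*Protocol*

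**What the plan says.** All the dosing rules at issue are in Protocol Section 4.2.4.

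- **Myocarditis row of Table 4.** The row reads "Myocarditis | Grade 1 or 2 | Withhold". At Grade 3 or 4 the action is permanent discontinuation. Corticosteroids are given according to severity. The row has no restart rule.
- **General instruction 2.** Its scope is "For situations where pembrolizumab has been withheld", with no event excepted. In those cases "pembrolizumab can be resumed after AE has been reduced to Grade 1 or 0 and corticosteroid has been tapered". It then requires permanent discontinuation if the event has not resolved within 12 weeks of the last dose, or if the steroid dose cannot be brought low enough in that time.
- **General instruction 1.** "Corticosteroid taper should be initiated upon AE improving to Grade 1 or less and continue to taper over at least 4 weeks".
- **NOTE after Table 4.** This is the only event-specific change to the restart grade. It begins "For participants with Grade 3 or 4 immune-related endocrinopathy where withhold of pembrolizumab is required" and allows restart at Grade 2 or below once the endocrinopathy is controlled by hormone replacement or, for type 1 diabetes, metabolic control has been achieved. It does not cover myocarditis.

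Two other places bear on the point. Section 1.4 names the event among the less common risks of pembrolizumab ("sarcoidosis, and myocarditis (some fatal"). The rechallenge note in Section 6.2.4 covers an event that was serious and possibly caused by trial treatment, or a re-exposure that carries significant added risk. In those cases, "the rechallenge must be approved in advance by the Sponsor as per dose modification guidelines in the protocol".

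**The concern.** The myocarditis row has the lowest hold threshold in the table, which suggests that the authors wanted more caution here than for other graded immune-related events. The general restart rule suits events first held at Grade 2 or higher, because a fall to Grade 1 then takes the patient below the hold. For myocarditis it does not. A patient can meet the restart condition while still at a grade that the row tells the investigator to hold.

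What is at stake is safety. The protocol itself describes the event as sometimes fatal, yet its written threshold allows re-dosing while the event is still present. Up to 7 centers may recruit (Section 4.1), and two sites could read the same table differently. No estimate, test or sample-size figure depends on this.

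**Working it through.** No formula or stated figure is involved. The check sets the grades at which each row withholds against the grades at which General instruction 2 allows restart, which are {0, 1}.

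Table 4 has ten event rows. Hypothyroidism only ever continues treatment, which leaves nine rows with a withhold action:

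| Table 4 row | Stated hold grades | Overlap with {0, 1} |
|---|---|---|
| Pneumonitis | 2 | none |
| Diarrhea/colitis | 2, 3 | none |
| AST/ALT or bilirubin | 2 | none |
| T1DM/hyperglycemia | hyperglycemia 3, 4; new-onset T1DM has no grade | none stated |
| Hypophysitis | 2; 3 or 4 (withhold or discontinue) | none |
| Hyperthyroidism | 3 or 4 (withhold or discontinue) | none |
| Nephritis/renal dysfunction | 2 | none |
| **Myocarditis** | **1, 2** | **1** |
| All other irAEs | intolerable or persistent 2; 3 (withhold or discontinue) | none |

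**Step 1: the general rule.** In eight of the nine rows every stated hold grade is 2 or higher, so restart at Grade 0 or 1 lies below it. Only myocarditis overlaps, at Grade 1.

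**Step 2: the NOTE.** For Grade 3 or 4 endocrinopathy the restart grades become {0, 1, 2}. The hypophysitis row holds at Grade 2, so there is an overlap at Grade 2 there. Hyperthyroidism continues at Grade 2 and hyperglycemia is held only from Grade 3, so the NOTE creates no overlap for them. The hypophysitis overlap is written out as an exception and carries its own condition, hormonal control. Myocarditis has no such exception or condition.

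**Step 3: follow one patient.** Myocarditis appears at Grade 2 and pembrolizumab is withheld under the row. Steroids are given, the event improves to Grade 1, and the taper is completed under instruction 1. Instruction 2 now allows restart. The event is at Grade 1, for which the row says withhold. Nothing in the row, the table footnote or the NOTE says which instruction governs.

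**Step 4: the grade that satisfies both rules.** The row holds at {1, 2} and discontinues at {3, 4}. The only grade left is 0, which is also within the restart set {0, 1}. Grade 0 is therefore the only restart point consistent with both instructions as written.

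**Step 5: an event that starts at Grade 1.** Instruction 2 speaks of an event being reduced to Grade 1 or 0. An event that began at Grade 1 and stayed there has not been reduced, so the rule is unclear for this patient and cannot be called permissive.

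**The case against.** The strongest reply is that an onset trigger and a restart threshold need not match. A new, untreated Grade 1 myocarditis of unknown course differs from one brought down from Grade 2 by treatment and a taper, and the hypophysitis exception shows that the protocol sometimes accepts restart at a hold grade. This is fair as far as it goes: overlap alone is not an error. But where the authors wanted that result, they wrote it as an exception and attached a condition. For myocarditis it arises only because a general rule meets a row with a lower threshold.

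A second reply is that the row, being specific, overrides the general permission, so a patient at Grade 1 is still on hold. That is a reasonable reading and may be the intended one. The protocol does not state it, and the fix would do so.

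A third is that other safeguards exist: Sponsor approval of rechallenge (Section 6.2.4), withdrawal by the investigator or for unacceptable adverse experiences (Section 4.8), and review by an independent medical monitor (Section 9.8.2). These stand and lower the risk. However, the Sponsor approval is tied to the dose modification guidelines, and the unacceptable-experience criterion refers to Section 4.2.4, so both lead back to the table that contains the conflict.

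Four stronger readings might be inferred, and the documents do not support them:

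- *The protocol directs sites to re-dose during myocarditis.* It does not. The restart wording is permissive, and an investigator may keep holding.
- *Myocarditis is the only place where restart is allowed at a hold grade.* It is the only overlap with the general rule. The NOTE creates another, by express exception, for hypophysitis.
- *The 12-week stop fails to catch this patient because a fall to Grade 1 counts as resolution.* Section 6.1.7.4 does follow events "until the resolution of the AE to Grade 0-1", but that concerns follow-up after treatment and names a target grade. Instruction 2 names none, so its meaning is open. The point does not depend on it: on either reading, the 12-week stop does not prevent a restart at Grade 1 before week 12.
- *Trial results are at risk.* Nothing here affects the primary or survival analyses.

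**Conclusion.** The concern holds as a gap in the safety instructions. Table 4 gives two answers for a myocarditis that has improved from Grade 2 to Grade 1 with steroids tapered: withhold under the row, and may resume under General instruction 2. This affects one of nine rows with a withhold action, at one grade.

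The conclusion assumes that instruction 2 applies to every withheld case, as its wording says, and that no unstated convention lets the row prevail. The documents give no rate for myocarditis, so no probability is claimed; that it will be rare among 24 patients is an assumption, in keeping with its place among the less common risks in Section 1.4. The rule is permissive, Sponsor approval may intervene, and efficacy is unaffected. It is a cheap improvement for patient safety, of low priority.

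**What to change.** Make two edits to Table 4 in the next protocol amendment:

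1. In General instruction 2, add that the restart rule applies unless the row states otherwise.
2. In the myocarditis row, state that pembrolizumab may resume only at Grade 0 with corticosteroids tapered, and is otherwise permanently discontinued at 12 weeks.

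Grade 0 is proposed because it is the one grade that the row neither holds nor stops. The medical lead may prefer a stricter rule, such as no restart after any myocarditis; either choice removes the conflict.

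The cost is one clause and one table cell, with no added procedures, visits or patients. The downside is that a rare patient with persistent Grade 1 myocarditis, who could be re-dosed under the present general rule, would lose pembrolizumab.
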